10.6.7. Sequential Organ Failure Assessment (SOFA) score

The score will be calculated on a daily basis. Adrenergic agents that do not appear in [Vincent](#), 1996 and for which a highest dose has been recorded, will be assigned a SOFA score of 2. Zero points are assigned if none of the points scoring criteria are met. If any of the information required to derive an individual SOFA component score is missing or cannot be obtained, then that component score will be set to a missing value.

The SOFA score will be calculated by summing the individual component scores (individual components derived as below). Note: Central Nervous System component will not be used in deriving the SOFA score in Study 205821:

SOFA Score / Variable (x)	0	1	2	3	4
Respiration: $P_{a}O_2/F_{i}O_2$ (mmHG)	$x \geq 400$	$300 \leq x < 400$	$200 \leq x < 300$	$100 \leq x < 200$	$x < 100$
				With Respiratory support (Note: if $P_{a}O_2/F_{i}O_2$ in these categories but subject not on respiratory support then a score of 2 should be assigned)	
Coagulation: Platelets (10^3 / mm 3)	$x \geq 150$	$100 \leq x < 150$	$50 \leq x < 100$	$20 \leq x < 50$	$x < 20$
Liver: Bilirubin (μ mol/L)	$x < 20$	$20 \leq x < 33$	$33 \leq x < 102$	$102 \leq x < 204$	$x \geq 204$
Cardiovascular : Hypotension (Adrenergic agents administered for at least one hour; doses are in μ g/kg/min)	Mean Arterial Pressure ≥ 70 mmHg	Mean Arterial Pressure < 70 mmHg	Dopamine ≤ 5.0 (μ g/kg/min) or any dose of: Dobutamine Or any dose of an adrenergic agent not listed here or in Vincent (1996)	Dopamine 5.1-15.0 (μ g/kg/min) or Epinephrine ≤ 0.1 or Norepinephrine ≤ 0.1	Dopamine > 15.0 (μ g/kg/min) or Epinephrine > 0.1 or Norepinephrine > 0.1
Central Nervous System: Glasgow Coma Score	$x \geq 15$	$13 \leq x \leq 14$	$10 \leq x \leq 12$	$6 \leq x \leq 9$	$x < 6$
Renal: Creatinine (μ mol/L)	$x \leq 110$	$110 < x \leq 170$	$170 < x \leq 300$	$300 < x \leq 440$ [Or Urine output < 500 mL/day]	$x > 440$ [Or Urine output < 200 mL/day]
Note: Central Nervous System scoring algorithm has been included above for completeness but in Study 205821 it is not expected to form part of the overall SOFA total					

In the SI.CONMEDS record (for vasopressors) the units may have to be converted from μ g/min to μ g/kg/min dose by merging on the weight from the vital signs dataset (and other unit conversions may be required for the other SOFA components).

$P_{a}O_2/F_{i}O_2$ values from the eCRF form should be double checked for accuracy (e.g. visual inspection of raw datasets to determine if they in the expected ranges for the stated unit).

10.6.8. Oxygen Saturation

The oxygen saturation may be calculated from the provided ratio SaO₂/FiO₂ readout if the eCRF field for Oxygen Saturation (Vitals eCRF) is blank or missing.

10.6.9. Calculation of PaO₂ / FiO₂ and SpO₂ / FiO₂

If required (e.g. because the automatically calculated eCRF field is blank or the units used in the auto-derived field appear to be incorrect) and sufficient source data are available then:

- The PaO₂/FiO₂ endpoint can be calculated when patients are intubated and have an arterial line present. Prior to computing the ratio the PaO₂ may need to be converted from kPa units to mmHg using the conversion rate 1/0.133. FiO₂ should be expressed as a proportion and not a percentage when deriving the ratio.
- SpO₂/ FiO₂ will be calculated as a ratio of percentages.

10.6.10. Construction of ARDATA.ALLCVTS

Guidance on the structure of the master A&R dataset that will hold potential covariate variables (for use in model building) is contained in [Table 9](#).

Table 9 Suggested Metadata for ARADTA.ALLCVTS (Modifications may be made if required, e.g. to add/remove variables based on questions arising from observed data – the HARP metadata form would capture the final specification used). SAS label text and units to be added as appropriate to the data item.

Type	Variable Name	Details	Suggestions for derivation / data source
Info	STUDYID	STUDYID	ARADATA.CV (Unique list of subjid, centreid and visitnum combinations where at least one PASP and/or RV Size Ratio result was evaluable in CMANALFL=1 records)
Info	SUBJID	SUBJID	
Info	USUBJID	USUBJID	
Info	CENTREID	CENTREID	VISITNUM 20.00 = DAY 1
Info	INVID	INVID	VISITNUM 30.00 = DAY 2
Info	VISITNUM	VISITNUM	VISITNUM 40.00 = DAY 3
Info	VISIT	VISIT	
Info	SUBJLEV	Extraction of set of subject level records	Only a single flag of 1 allowed per subject. Usually Day 1 record if present, day 2 (or 3) otherwise
Subject	AGE	Age at Screening	ARADATA.DEMO (AGE)
Subject	SEX	Sex	ARADATA.DEMO (SEX)
Subject	VSBMI	BMI at Screening	ARADATA.VITALS (VSBMI)
Subject	SAPSII	SAPS II at Screening	DMDATA.CC (Select CCORRSN where CCTESTCD=CC001)
Subject	RSINTU	Reason for Intubation at Screening (Categorical)	ARADATA.PR (Select the derived variable PRMIND which contains the mapping of the free text variable (PRINDC) for reason for intubation at screening visit (VISITNUM=10); see Section 10.6.4)
Time	INTUI	Intubated by Study Day (Binary Y/N)	ARADATA.PR (Where PRTREAT=INTUBATION & VISITNUM in (20,30,40)) For each subject and visitnum match: Set corresponding INTUI to Y if PROCCUR = Y for Day ; Set to N otherwise
Subject	ARDSX	ARDS Diagnosis at any time (Binary Y/N)	DMDATA.FACE (Where FCETSTCD=FCEBU001) Set to Y if Any of FCEORSCD = ZZY for a subject; Set to N otherwise

Type	Variable Name	Details	Suggestions for derivation / data source
Time	ARDSI	ARDS Diagnosis by Study Day (Binary Y/N)	DMDATA.FACE (Where FCETSTCD=FCEBU001) Treat any Screening results as being from Day 1 (use the worst case outcome as Day 1 result). For each subject and visitnum match: Set corresponding ARDSI to Y if FCEORSCD = ZZY for Day ; Set to N otherwise Note: Class any SCREENING result as DAY 1 record for the purposes of ARDS diagnosis
Subject	INOX	Inhaled Nitric Oxide at any time (Binary Y/N)	DMDATA.FACM (Where FCMTSTCD=FCMAX001) Set to Y if Any of FCMORSCD = ZZY for a subject; Set to N otherwise
Time	INOI	Inhaled Nitric Oxide by Study Day (Binary Y/N)	DMDATA.FACM (Where FCMTSTCD=FCMAX001) Treat any Screening results as being from Day 1 (use the worst case outcome as Day 1 result). For each subject and visitnum match: Set corresponding INOI to Y if FCMORSCD = ZZY for Day ; Set to N otherwise
Subject	VASOX	Vasopressor, Inotrope or other Vasoactive agent at any time (Binary Y/N)	DMDATA.FACM (Where FCMTSTCD=FCMAX002) Set to Y if Any of FCMORSCD = ZZY for a subject; Set to N otherwise
Time	VASOI	Vasopressor, Inotrope or other Vasoactive agent by Study Day (Binary Y/N)	DMDATA.FACM (Where FCMTSTCD=FCMAX002) Treat any Screening results as being from Day 1 (use the worst case outcome as Day 1 result). For each subject and visitnum match: Set corresponding VASOI to Y if FCMORSCD = ZZY for Day ; Set to N otherwise
Subject	PRONEX	Proned at any time (Binary Y/N)	ARDATA.PR (Where PRTREAT=MECHANICAL VENTILATION; exclude records with PRREFID=SOFA) Set to Y if Any of Subjects records have PRONE=Y

Type	Variable Name	Details	Suggestions for derivation / data source
Time	PRONEI	Proned by Study Day (Binary Y/N)	ARDATA.PR (Where PRTREAT=MECHANICAL VENTILATION & VISITNUM in (20,30,40); exclude records with PRREFID=SOFA) For each subject and visitnum match: Set corresponding PRONEI to Y if PRONE = Y for Day ; Set to N otherwise
Subject	ECMOX	ECMO at any time (Binary Y/N)	ARDATA.PR (Where PRTREAT= EXTRACORPOREAL MEMBRANE OXYGENATION) Set to Y if Any of Subjects records have PROCCUR=Y
Time	ECMOI	ECMO by Study Day (Binary Y/N)	ARDATA.PR (Where PRTREAT= EXTRACORPOREAL MEMBRANE OXYGENATION & VISITNUM in (20,30,40)) For each subject and visitnum match: Set corresponding ECMOI to Y if PROCCUR = Y for Day ; Set to N otherwise
Subject	ECCO2RX	ECCO2R at any time (Binary Y/N)	ARDATA.PR (Where PRTREAT= EXTRACORPOREAL CO2 REMOVAL) Set to Y if Any of Subjects records have PROCCUR=Y
Time	ECCO2RI	ECCO2R by Study Day (Binary Y/N)	ARDATA.PR (Where PRTREAT= EXTRACORPOREAL CO2 REMOVAL & VISITNUM in (20,30,40)) For each subject and visitnum match: Set corresponding ECCO2RI to Y if PROCCUR = Y for Day ; Set to N otherwise
Subject	LCOND ^T	Last Contact Date (Date)	ARDATA.DS (Where DSSCATCD=4 & VISITNUM=0) Select DSSTDT
Subject	LCONDY	Last Contact Study Day (Continuous)	ARDATA.DS (Where DSSCATCD=4 & VISITNUM=0) Select DSSTDY
Subject	FUDT	Date of Follow Up Visit (Date)	DMDATA.VISIT (Where VISITNUM=50) Select VISITDT

Type	Variable Name	Details	Suggestions for derivation / data source
Subject	DTHHOSP	In hospital mortality (Categorical Y/N/U)	DMDATA.SS (Where VISITNUM=50 & SSTESTCD=AD009) Set to Y if SSORRSCD=ZZY; to N if SSORRSCD=ZZN and to U if SSORRSCD=ZZUNK
Subject	DERDTHDT	Derived Death Date (Date)	Set to the earliest of the dates obtained from... DMDATA.DTH (match on SUBJID and select DDDT) Or LCOND variable if DTHHOSP = Y Or If no dates located above but subject has DMDATA.STATUS DTHBWIN=Y then set to a derived date corresponding to day 3 (relative to that subjects date of 1 st echo) Otherwise set to missing
Subject	DERDTHDY	Derived Death Study Day (Continuous)	The study day of the DERDTHDT (relative to time zero – the date of 1 st echo) Set to missing if DERDTHDT = missing
Subject	DTH28	Death by Day 28 (Categorical Y/N/U)	Set to Y if DERDTHDY not missing & \leq 28 Set to N if [DERDTHDY = missing & LCONDY \geq 28] or [DERDTHDY \geq 28] Set to U otherwise
Subject	SURVIND	Survival Censoring Indicator (Categorical)	Set to 0 if DERDTHDT not missing Set to 1 (censored time) otherwise <Note: Indicator variable should be used in conjunction with LCONDY in any time to event analyses>
Subject	ICUDY	Length of stay (days) in ICU (Continuous)	DMDATA.HRU (Where HUCLVCD=4) Select HUNDYCAR
Subject	HOSPDY	Length of stay (days) in Hospital (Continuous)	DMDATA.HRU (Where HUCLVCD=8) Select HUNDYCAR

Type	Variable Name	Details	Suggestions for derivation / data source
Subject	DYWVNT	Ventilation Free Days (1 to 28) (Continuous)	DMDATA.HRU (Where HUSCATCD=3) Select DYWVNT
Subject	SGX1TO3	Any Surgery between Day 1 and Day 3 (Binary Y/N)	DMDATA.SURGERY (Where VISITNUM=50) Select SPYN
Time	RVDYSI	Single variable capturing RV Dysfunction Status by Study Day (Categorical: 1=No PCD 2=Moderate PCD (not severe enough to qualify as ACP) 3 = Non-severe ACP 4 = Severe ACP)	ARDATA.CV (Where CVANALFL=1 & CVTSTCD in (AK015, AK016)) For each subject and visitnum match Set to: 
• 1 if CVTSTCD=AK015 & CVORRSCD=N• 2 if [CVTSTCD=AK015 & CVORRSCD=Y] & [CVTSTCD=AK016 & CVORRSCD=51]• 3 if [CVTSTCD=AK015 & CVORRSCD=Y] & [CVTSTCD=AK016 & CVORRSCD=52]• 4 if [CVTSTCD=AK015 & CVORRSCD=Y] & [CVTSTCD=AK016 & CVORRSCD=53]
Subject	RVDYSX	Single variable capturing Worst observed RV Dysfunction Status at any time (Categorical)	MAX of RVDYSI variable (group by SUBJID)
Subject	PCDACPX	Any PCD or ACP at any time in study (Binary Y/N)	Set to Y if RVDYSX in (2,3,4) Set to N otherwise
Time	PCDACPI	Any PCD or ACP by Study Day (Binary Y/N)	Set to Y if RVDYSI in (2,3,4) Set to N otherwise
Subject	NORVDYSX	Did not have PCD or ACP at any time in study (Binary Y/N)	Set to Y if RVDYSX = 1 Set to N otherwise
Time	NORVDYSI	Did not have PCD or ACP on Study Day (Binary Y/N)	Set to Y if RVDYSI = 1 Set to N otherwise
Subject	PCDX	Worst case was PCD at any time in study (Binary Y/N)	Set to Y if RVDYSX = 2 Set to N otherwise
Time	PCDI	PCD on Study Day (Binary Y/N)	Set to Y if RVDYSI = 2 Set to N otherwise

Type	Variable Name	Details	Suggestions for derivation / data source
Subject	ACPX	Worst case was ACP at any time in study (Binary Y/N)	Set to Y if RVDYSX = 3 Set to N otherwise
Time	ACPI	ACP on Study Day (Binary Y/N)	Set to Y if RVDYSI = 3 Set to N otherwise
Subject	SEVACPX	Worst case was Severe ACP at any time in study (Binary Y/N)	Set to Y if RVDYSX = 4 Set to N otherwise
Time	SEVACPI	Severe ACP on Study Day (Binary Y/N)	Set to Y if RVDYSI = 4 Set to N otherwise
Subject	ARDNOX	ARDS but no PCD or ACP at any time in study (Binary Y/N)	Set to Y if [ARDSX=Y & NORVDYSX=Y] Set to N otherwise
Subject	ARDPCDX	ARDS and worst case PCD at any time in study (Binary Y/N)	Set to Y if [ARDSX=Y & PCDX =Y] Set to N otherwise
Subject	ARDACPX	ARDS and worst case ACP at any time in study (Binary Y/N)	Set to Y if [ARDSX=Y & ACPX =Y] Set to N otherwise
Subject	ARDSACPX	ARDS and worst case Severe ACP at any time in study (Binary Y/N)	Set to Y if [ARDSX=Y & SEVACPX =Y] Set to N otherwise
Time	GII	Global Inhomogeneity Index (Continuous)	DMDATA.CC (Select CCORRSN where CCTESTCD=BY001 & VISITNUM in (20,30,40))

Type	Variable Name	Details	Suggestions for derivation / data source
Time	<Various Vital Signs> SYSBP DIABP HEART TEMP RESP VSPO2BLD VSMAP VSPPV	Take names/properties directly from dataset (Continuous)	DMDATA.VITALS (Where VISITNUM in (20,30,40) & VSREFID ^= SOFA) Select (use same name) SYSBP DIABP HEART TEMP RESP VSPO2BLD VSMAP VSPPV Match on subjid and visitnum
Time	OI	Oxygenation Index (Continuous)	DMDATA.RE (Where VISITNUM in (20,30,40) & RETESTCD=AC002) Select REORRSN Match on subjid and visitnum
Time	PAO2	Partial pressure of arterial O2 (mmHg) (Continuous)	DMDATA.LAB (Where VISITNUM in (10,20,30,40) & LBREFID ^=SOFA & LBTESTCD=PAO2_BLP) For each subject select the most recent non-missing value from visitnum 10,20 (and set result to have visitnum=20) prior to merging by subject and visitnum Select LBORRESN
Time	PAO2DM	DateTime of PAO2 Sample (DateTime)	DMDATA.LAB (Where VISITNUM in (10,20,30,40) & LBREFID ^=SOFA & LBTESTCD=PAO2_BLP) For each subject select the most recent non-missing LBORRESN value from visitnum 10,20 (and set result to have visitnum=20) prior to merging by subject and visitnum Combine LBDT and LBACTM into a single datetime formatted variable

Type	Variable Name	Details	Suggestions for derivation / data source
Time	PACO2	Carbon dioxide partial pressure (mmHg) (Continuous)	DMDATA.LAB (Where VISITNUM in (10,20,30,40) & LBREFID ^=SOFA & LBTESTCD=PCO2_BLP) For each subject select the most recent non-missing value from visitnum 10,20 (and set result to have visitnum=20) prior to merging by subject and visitnum Select LBORRESN
Time	LA ^T	Serum Lactate (mmol/L) (Continuous)	DMDATA.LAB (Where VISITNUM in (10,20,30,40) & LBREFID ^=SOFA & LBTESTCD=LACT_PLC) For each subject select the most recent non-missing value from visitnum 10,20 (and set result to have visitnum=20) prior to merging by subject and visitnum Select LBORRESN
Time	HC03	Serum Bicarbonate (mEq/L) (Continuous)	DMDATA.LAB (Where VISITNUM in (10,20,30,40) & LBREFID ^=SOFA & LBTESTCD=HC03_PLC) For each subject select the most recent non-missing value from visitnum 10,20 (and set result to have visitnum=20) prior to merging by subject and visitnum Select LBORRESN
Time	PH	Blood pH (Continuous)	DMDATA.LAB (Where VISITNUM in (10,20,30,40) & LBREFID ^=SOFA & LBTESTCD=PH_BLG) For each subject select the most recent non-missing value from visitnum 10,20 (and set result to have visitnum=20) prior to merging by subject and visitnum Select LBORRESN
Time	BASEXA	Base excess (arterial whole blood) (mEq/L) (Continuous)	DMDATA.LAB (Where VISITNUM in (10,20,30,40) & LBREFID ^=SOFA & LBTESTCD=BASEXA_BLC) For each subject select the most recent non-missing value from visitnum 10,20 (and set result to have visitnum=20) prior to merging by subject and visitnum Select LBORRESN

Type	Variable Name	Details	Suggestions for derivation / data source
Time	BDEFA	Base deficit (arterial whole blood) (mEq/L) (Continuous)	DMDATA.LAB (Where VISITNUM in (10,20,30,40) & LBREFID ^=SOFA & LBTESTCD=BDEFA_BLC) For each subject select the most recent non-missing value from visitnum 10,20 (and set result to have visitnum=20) prior to merging by subject and visitnum Select LBORRESN
Time	TROPI	Troponin I (UG/L) (Continuous)	DMDATA.LAB (Where VISITNUM in (10,20,30,40) & LBREFID ^=SOFA & LBTESTCD=TROPI_PLC) For each subject select the most recent non-missing value from visitnum 10,20 (and set result to have visitnum=20) prior to merging by subject and visitnum Select LBORRESN
Time	TROPT	Troponin T (UG/L) (Continuous)	DMDATA.LAB (Where VISITNUM in (10,20,30,40) & LBREFID ^=SOFA & LBTESTCD=TROPT_PLC) For each subject select the most recent non-missing value from visitnum 10,20 (and set result to have visitnum=20) prior to merging by subject and visitnum Select LBORRESN
Time	PFSOFA	PaO2/FiO2 entered onto SOFA form (Continuous)	DMDATA.LAB (Where VISITNUM in (10,20,30,40) & LBREFID =SOFA & LBTESTCD=PAO2FI_BLQ) For each subject select the most recent non-missing value from visitnum 10,20 (and set result to have visitnum=20) prior to merging by subject and visitnum Select LBORRESN
Time	FIO2	Fraction of Inspired Oxygen (%) (Continuous)	DMDATA.FAPR (Where VISITNUM in (20,30,40) & FPRSTCD=FPRAW005) Select FPRORSN. Match on subjid and visitnum

Type	Variable Name	Details	Suggestions for derivation / data source
Time	FIO2DM	DateTime of FIO2 Sample (DateTime)	DMDATA.FAPR (Where VISITNUM in (20,30,40) & FPRSTCD=FPRAW005) Combine FPRDT and FPRTM into a single datetime formatted variable Match on subjid and visitnum
Time	PFDIFF	Difference between PaO2 and FiO2 Sampling occasions (mins)	(PAO2DM - FIO2DM) converted into minutes
Time	PFECRF	PaO2/FiO2 derived (Continuous)	PAO2 / (FIO2 / 100)
Time	PFECRF30	PaO2/FiO2 (sampling within ± 30 mins) (Continuous)	Select PFECRF if $ABS(PFDIFF) \leq 30$; set to missing otherwise
Time	FPRBH001	Static Respiratory System Compliance (mL/cm H ₂ O) (Continuous)	DMDATA.FAPR (Where VISITNUM in (20,30,40) & FPRSTCD= FPRBH001) Select FPRORSN. Match on subjid and visitnum
Time	FPRBH003	Pressure Support Ventilation (Binary Y/N)	DMDATA.FAPR (Where VISITNUM in (20,30,40) & FPRSTCD= FPRBH003) Match on subjid and visitnum Set Y if FPRORSCD=ZZY Set N otherwise
Time	FPRAB001	Tidal Volume (mL) (Continuous)	DMDATA.FAPR (Where VISITNUM in (20,30,40) & FPRSTCD= FPRAB001) Select FPRORSN. Match on subjid and visitnum
Time	FPRAB002	Positive End Expiratory Pressure PEEP (cm H ₂ O) (Continuous)	DMDATA.FAPR (Where VISITNUM in (20,30,40) & FPRSTCD= FPRAB002) Select FPRORSN. Match on subjid and visitnum
Time	FPRAB003	Peak Ventilatory Pressure (cm H ₂ O) (Continuous)	DMDATA.FAPR (Where VISITNUM in (20,30,40) & FPRSTCD= FPRAB003) Select FPRORSN. Match on subjid and visitnum
Time	FPRAB008	Plateau Ventilatory Pressure (cm H ₂ O) (Continuous)	DMDATA.FAPR (Where VISITNUM in (20,30,40) & FPRSTCD= FPRAB008) Select FPRORSN. Match on subjid and visitnum

Type	Variable Name	Details	Suggestions for derivation / data source
Time	FPRBH004	Mean Airway Pressure (cm H2O) (Continuous)	DMDATA.FAPR (Where VISITNUM in (20,30,40) & FPRSTCD= FPRBH004) Select FPRORSN. Match on subjid and visitnum
Time	FPRBH005	Driving Pressure (cm H2O) (Continuous)	DMDATA.FAPR (Where VISITNUM in (20,30,40) & FPRSTCD= FPRBH005) Select FPRORSN. Match on subjid and visitnum
Time	<Various Echo endpoints and the key RAS peptides>	Take from source dataset	ARDATA.STATSCAT (drop STUDYID, CENTREID, INVID, INVNAME, AGE, SEX, RACE, RACECD, ATRTCD, ATRTGRP, TRTCD, TRTGRP, USUBJID, VISIT, AH001AC, AK015, AK016 variables) Select remaining variables and match on subjid and visitnum

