9.5.3. Disease diagnosis

Diagnosis of ARDS, PCD and ACP.

- ACP is defined as a dilated RV in the mid-esophagus longitudinal view or apical 4-chamber view [end-diastolic RV / left ventricle (LV) area ratio (0.6)] associated with the presence of a septal dyskinesia in the (transgastric) short-axis view of the heart.
- Severe ACP is defined as severely dilated RV (end-diastolic RV / LV area ratio ≥ 1) with septal dyskinesia. Septal dyskinesia will be particularly sought at end-systole, while analysing loops in slow motion.
- PCD is defined as moderate dysfunction (PASP [>40 mmHg] or a dilated RV end-diastolic RV / left ventricle (LV) area ratio [≥ 0.6] but without septal dyskinesia). In case of the inability of measuring transtricuspid pressure gradient, pulmonary hypertension will be defined as a Tacc below 100 ms.
- ARDS is defined as per the Berlin definition ([Ranieri 2012](#)):

Timing	Within 1 week of a known clinical insult or new or worsening respiratory symptoms
Chest imaging	Bilateral opacities—not fully explained by effusions, lobar/lung collapse, or nodules
Origin of edema	Respiratory failure not fully explained by cardiac failure or fluid overload Need objective assessment (eg, echocardiography) to exclude hydrostatic edema if no risk factor present
Oxygenation	
Mild	$200 \text{ mm Hg} < \text{PaO}_2/\text{FIO}_2 \leq 300 \text{ mm Hg}$ with PEEP or CPAP $\geq 5 \text{ cm H}_2\text{O}$
Moderate	$100 \text{ mm Hg} < \text{PaO}_2/\text{FIO}_2 \leq 200 \text{ mm Hg}$ with PEEP $\geq 5 \text{ cm H}_2\text{O}$
Severe	$\text{PaO}_2/\text{FIO}_2 \leq 100 \text{ mm Hg}$ with PEEP $\geq 5 \text{ cm H}_2\text{O}$

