4. ANALYSIS POPULATIONS

Population ¹	Definition / Criteria	Analyses Evaluated
Screened	All participants who have been screened.	
• To aid construction of Consort diagram in any publication
Enrolled	All participants who had passed screening and who had appropriate informed consent (via any of the processes described in the protocol).	
• Summary of Subject Status and Reason for Study Withdrawal• Summary of Study Populations• Summary of Exclusions from the

Population ¹	Definition / Criteria	Analyses Evaluated
		Safety/Completed/ Evaluable Populations
Safety	All participants for whom at least one echocardiograph and/or blood sample has been taken, and who did not retrospectively withdraw the consent.	
 • Study population (excl. specific tables mentioned below) • Safety
Evaluable	All participants for whom PASP, RV size ratio, Ang II and Ang(1-7) data have been recorded for at least one study time point, and who did not retrospectively withdraw the consent (and who still had at least one study time point of data remaining after accounting for any prohibited concomitant medications (for example but not limited to renin inhibitors, ARBs or ACE inhibitors) – See Section 10.1.1).	
 • Pharmacodynamic/ Biomarker (excl. disease diagnosis status)
Evaluable with Prohibited Con Meds	All participants in the Evaluable population plus any participants who were excluded from the Evaluable population because of prohibited concomitant medications (for example but not limited to renin inhibitors, ARBs or ACE inhibitors)	
 • Sensitivity for Primary analysis (conditional on number of prohibited con meds)
Completed ²	All participants for whom PASP, RV size ratio, Ang II, and Ang(1-7) data have been recorded for all three study days.	
 • Disease diagnosis status
At Risk	
For the purpose of evaluating ACP/PCD and ARDS incidence rates the participants who satisfy
 
1) PASP and RV size ratio recorded for all three study days (regardless of the Ang II and Ang(1-7) status)
 
and/or
 
2) databased ACP/PCD and/or ARDS assessment during the study period (even if they do not have three days' worth of study assessments for the above echo outcomes)
 
provided consent is not withdrawn.
	
 • Disease diagnosis status

NOTES :

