5.3. Examination of Covariates, Other Strata and Subgroups

5.3.1. Covariates and Other Strata

The set of potential covariates and other strata that may be used in descriptive summaries and statistical analyses, some of which may also be used for subgroup analyses are large.

To facilitate flexible model building and analyses a A&R dataset(s) of potential covariate and grouping variables should be constructed (called ARDATA.ALLCVTS). It would be expected to contain three records per participant (Study Day 1, Day 2 and Day 3 values for time-varying covariates), with subject-level covariates repeated across the three records (a flagging variable should also be created to subset the main dataset to extract one record per subject if analyses only involve subject-level covariates); an illustrative example is shown below

Subject	Visit	SUBJLEV	AGE	SEX	SAPSII	ARDSX	ARDSI	...
PPD	Day 1	1	35	M	12	N	N	...
	Day 2	0	35	M	12	N	N	...
	Day 3	0	35	M	12	N	N	...
	Day 1	1	43	F	16	Y	N	...
	Day 2	0	43	F	16	Y	Y	...
	Day 3	0	43	F	16	Y	Y	...
	Day 1...	1	54...	M...	7...	N...	N...	...

Guidance for its construction/algorithms are given in Section 10.6.10.

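### SAP Table 9 builds the ALLCVTS rows only from visits with an evaluable PASP or RV size ratio, so a PCD diagnosis recorded on a visit with neither measure never reaches the participant's worst-case status.

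*SAP*

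**What the plan says.** **Row rule.** SAP 10.6.10, Table 9, defines the ALLCVTS rows as the "Unique list of subjid, centreid and visitnum combinations where at least one PASP and/or RV Size Ratio result was evaluable". One of the two measures is enough to keep a visit.

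**Status variables.** RVDYSI is filled from the PCD/ACP records (AK015 and AK016 in ARDATA.CV) by matching on subject and visit. RVDYSX is the "MAX of RVDYSI variable (group by SUBJID"). PCDACPX, NORVDYSX, PCDX, ACPX and SEVACPX follow from RVDYSX, and their daily counterparts from RVDYSI. Each of these flags is N unless its condition is met.

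**ARDS.** The any-time flag ARDSX has no visit match: "Set to Y if Any of FCEORSCD = ZZY for a subject; Set to N otherwise". The daily flag ARDSI is matched by subject and visit.

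**Where the flags are used.** SAP 5.3.2 defines its subgroups by these ALLCVTS variables. SAP 5.3.1 says of the dataset: "It would be expected to contain three records per participant".

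**Diagnosis without PASP.** Protocol 9.5.3 provides: "In case of the inability of measuring transtricuspid pressure gradient, pulmonary hypertension will be defined as a Tacc below 100 ms".

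**Incidence.** Criterion 2 of the At Risk population (SAP 4) admits a participant with a "databased ACP/PCD and/or ARDS assessment during the study period", even without three days of the echo outcomes. SAP 7.2.2 counts visits, and participants, with any ARDS or PCD/ACP assessment.

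**The concern.** A row filter that suits the association models is applied before diagnosis status is derived. The association models cannot use a visit that lacks an echo outcome, but a diagnosis can be valid on such a visit. Because RVDYSX is a maximum over the retained rows, a missing row can lower the worst-case status and can never raise it. The flags then record the result as a definite N, with nothing to show that a positive visit was left out.

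At stake are the 5.3.2 subgroups and any display grouped by PCD/ACP status from ALLCVTS. Table 1.7 (demographics and baseline by PCD/ACP status, Safety population) is the clearest case. The SAP gives no other derivation of worst-case PCD/ACP status, so a programmer has no alternative rule to follow.

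**Working it through.** The plan states no figure for this point. The nearest is the ±5-point precision for ACP incidence in protocol 10.1. It reproduces as 1.96 × √(0.10 × 0.90 / 150) = 0.048, or 4.8 points. It concerns a different question and is not used below.

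**Step 1: can a protocol-conforming diagnosis lack both measures?**
- The Tacc route applies when the transtricuspid gradient cannot be measured.
- SAP 10.6.6, Table 7, sets PASP to missing whenever the gradient is missing.
- PCD called by this route therefore always lacks PASP, and the visit keeps a row only if the area ratio was obtained by TTE or TOE.
- ACP and severe ACP are defined with the area ratio, so an ACP visit should normally keep its row.

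The exposed diagnoses are thus mainly PCD on Tacc without a ratio, a diagnosis entered without a numeric ratio, and ARDS recorded on a visit without either echo value.

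**Step 2: apply Table 9 literally.** Four invented participants, to show direction only. Visits with neither PASP nor ratio are marked †.

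| Participant | Day 1 | Day 2 | Day 3 | ARDS recorded |
|---|---|---|---|---|
| A | No PCD | PCD † | No PCD | Day 2 |
| B | PCD † | no visit | no visit | Day 1 |
| C | No PCD | No PCD | ACP | none |
| D | PCD | PCD † | No PCD | none |

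| Result | Table 9 rows | All databased diagnoses |
|---|---|---|
| Participants / visits | 3 / 7 | 4 / 10 |
| PCDACPX = Y (participants) | 2 | 4 |
| PCDACPI = Y (visits) | 2 | 5 |
| ARDSX = Y (participants) | 1 | 2 |
| ARDSI = Y (visits) | 0 | 2 |

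- **A** loses the only positive visit. RVDYSX is 1, PCDACPX is N and NORVDYSX is Y. ARDSX stays Y, so the joint category becomes ARDS without PCD or ACP instead of ARDS with PCD. ARDSI for Day 2 is gone.
- **B** has no row, hence no PCD/ACP status and no ARDSX, although one echocardiogram or blood sample is enough for the Safety population and criterion 2 admits B to At Risk.
- **C** is unaffected.
- **D** loses a positive visit, but the worst case is unchanged because Day 1 is equally severe.

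**Step 3: size per participant.** Each participant like A lowers a whole-study proportion by 1/N:
- 1/30 = 3.3 points;
- 1/50 = 2.0 points;
- 1/150 = 0.7 points.

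N = 150 is the planned maximum. The values 30 and 50 are assumptions, because the study stopped early and the SAP gives no final number. The count of participants like A or B is not in the documents, so the total effect cannot be computed.

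**Step 4: compare with the counting rules.** If Table 4.1 were programmed from ALLCVTS, A's and B's positive visits would be missing from the numerators, while At Risk criterion 2 and SAP 7.2.2 count those participants and visits.

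**The case against.** The strongest reply is that ALLCVTS was never meant to carry the incidence analysis. The SAP calls it the "master A&R dataset that will hold potential covariate variables (for use in model building"), and Table 9 is suggested metadata: "Modifications may be made if required, e.g. to add/remove variables based on questions arising from observed data". SAP 7.2.2 has its own counting rule and an unnamed analysis dataset. Neither Table 4.1 nor Listing 15 names ALLCVTS, and the diagnoses remain in ARDATA.CV and DMDATA.FACE. This stands. A reader might infer that the PCD/ACP and ARDS incidence rates are biased downwards, but that needs a programming choice the SAP does not state. Even then, visit-level rates need not fall, because a dropped visit can leave the denominator too.

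Other tempting inferences also fail:
- *ARDS diagnoses are lost.* ARDSX is lost only for a participant with no row at all; otherwise only ARDSI is.
- *At Risk was created to keep diagnoses without echo values.* Its stated reason (note 2 to SAP 4) is independence from RAS biomarker availability. The mismatch rests on criterion 2 alone.
- *Carry-forward of categorical covariates (SAP 10.7.2) breaks.* That rule may draw on screening, which has no ALLCVTS row, so it must work from source data.
- *SAP 5.3.1 requires three records.* It only expects them and defers to 10.6.10, and the SUBJLEV rule foresees an absent Day 1.

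The reply does not remove the core. SAP 5.3.1 and 5.3.2 make ALLCVTS a source of grouping variables for descriptive summaries as well as models, and Table 9 is the only worst-case derivation given. Freedom to modify the table does not warn a programmer that following it gives a wrong status.

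**Conclusion.** The point holds in limited form. Followed literally, Table 9 misclassifies a participant whose only, or worst, positive visit lacks both PASP and RV size ratio, and it gives no status to a participant with no evaluable measure on any day. The consequence falls on the 5.3.2 subgroup variables, and on Table 1.7 where its columns are taken from ALLCVTS.

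The number of participants affected is unknown and may be small, since either measure by either echo route keeps a visit and ACP is rarely exposed. The 1/N figures show what one such participant would do; they do not estimate the impact. A reader might set them against the ±5-point precision, but that figure is for ACP at 10% incidence with 150 participants, whereas the exposed diagnosis is mainly PCD and the study stopped early.

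The conclusion assumes that Table 9 is programmed as written and that at least one PCD diagnosis was databased on a visit with neither measure. It is still worth correcting, because the error would be silent and the correct status can be derived from data already held.

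**What to change.** In SAP 10.6.10:
1. Derive RVDYSI and RVDYSX from all analysis-flagged AK015/AK016 records before any row restriction.
2. Build the ALLCVTS rows from every Day 1, 2 or 3 visit with an echo, RAS or PCD/ACP/ARDS assessment, and align the wording of 5.3.1 with that rule.
3. Keep a separate not-assessed value, so that a missing diagnosis is not coded N.
4. Apply the PASP/RV-evaluable condition only when selecting rows for the association models.
5. State that Tables 1.7 and 4.1 use the unrestricted diagnoses.

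The cost is a short edit to the dataset specification and a rerun. No new data are needed. A count of diagnosed visits with neither PASP nor RV size ratio, run at the same time, would show whether any result changes.
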